11.2 Data Analysis

Table 5 below details how data from the surveys will be analyzed.

Table 5: Details of how measurements will be analyzed

Measurement	General details on purpose of analysis	Specific details on analysis
Participant perspective surveys	Feeding system surveys at baseline and end of study, to assess participant perspectives on feeding system specific parameters and the impact of converting from usual system(s) to Mobility+	Surveys consist of 16 five-point Likert scale type questions, where rating options either range from very difficult to very easy, or strongly disagree to strongly agree. The ratings are assigned a point scoring system, whereby the most negative option (i.e. very difficult or strongly disagree) is assigned 0 points and the most positive option (i.e. very easy or strongly agree) is assigned 4, meaning the total possible maximum score is 64 points. As participants are asked to complete these surveys at baseline and at study end, the overall score obtained with their usual systems can be compared to the overall score obtained after using Mobility+. Scores for individual questions can also be compared.
QoL measures (QoL survey at baseline and QoL question at end of study)	A simple QoL measure will be used at baseline to gauge participants overall QoL using a scale previously published (See Appendix 5) accompanied by a simple question evaluating if self-perceived QoL has changed, at end of study	Determine baseline QoL Evaluate any changes to QoL in the second week of study

General End of Study Questions	
This survey is designed to assess changes in participants perceived wellbeing and mobility from study start – where they used their usual feeding system – to study end with Mobility+. It will also capture additional information on Mobility+ usage patterns and consumer demand for Mobility+.
	
The survey consists of 9 simple questions which predominantly assess change in participants perceived wellbeing and mobility with Mobility+ versus their usual systems. The questions are mostly Likert scale type questions where answer options range from “much better” to “much worse”. Additional questions assess the importance of mobility to the participant, how the participant wore the Mobility+ and if the participant would like to use the Mobility+ again, among others. Data collected will supplement QoL and participant perspectives data.

---------------------------------------	---	--

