Which type of feeding tube do you have?	G-tube 	J-tube 

Appendix 4
Participant perspectives baseline survey

 Participant perspectives of current feeding system: Usability, mobility and ease of use

(Operator asks the Participant these questions)

During use of your current feeding system, how do you find these activities?	Very Difficult	Difficult	Neutral	Easy	Very Easy	
Moving from one room to another room						
Going up and down stairs						
Short walk (e.g., one block)						
Long walk (e.g., several blocks)						
Travelling in car/public transport						
Moderate intensity physical activities, such as: - Moving a table - Pushing a vacuum - Bowling - Playing golf						
Other daily activities (e.g., lifting or carrying groceries, household chores)						
Ability to sleep						
Socializing with friends/family						
During use of your current feeding system, how do you find working/studying or both? Please log as N/A if participant does neither.	Very Difficult	Difficult	Neutral	Easy	Very Easy	N/A
Note to operator: When scoring this questionnaire, assign points using the legend below. Very Difficult = 0 points, Somewhat Difficult = 1, Neutral = 2, Somewhat Easy = 3 and Very Easy = 4						
Thinking about your overall experience with your current system, how strongly do you	Strongly Disagree	Some-what Disagree	Neutral	Some-what Agree	Strongly Agree	

agree or disagree with the following statements?					
My current system is easy to use					
My current system is easy to carry					
The noise level of my current system during use (including alarms) is acceptable					
My current system allows me to feed discreetly					
I am satisfied with the overall performance of my current system					
Note to operator: When scoring this questionnaire, assign points using the legend below. Strongly Disagree = 0 points, Somewhat Disagree = 1, Neutral = 2, Somewhat Agree = 3 and Strongly Agree = 4					
Do you experience any of the following symptoms of feed intolerance while using your current feeding system?					
Gas/Bloating?	 Yes			 No	
If yes, is it mild, moderate, or severe?	 Mild	 Moderate	 Severe		
Abdominal Pain?	 Yes			 No	

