experience with the Mobility+ system, how strongly do you agree or disagree with the following statements?	Strongly Disagree	Some-what Disagree	Neutral	Some-what Agree	Strongly Agree
The Mobility+ system is easy to use					
The Mobility+ system is easy to carry					
The silent nature of The Mobility+ system during use is acceptable					
The Mobility+ allows me to feed discreetly					
I am satisfied with the overall performance of the Mobility+ system					
Note to operator: When scoring this questionnaire, assign points using the legend below. Strongly Disagree = 0 points, Somewhat Disagree = 1, Neutral = 2, Somewhat Agree = 3 and Strongly Agree = 4					
Do you experience any of the following symptoms of feed intolerance while on your current feeding system?					
Gas/Bloating?	□ Yes			□ No	
If yes, is it mild, moderate, or severe?	Mild □	Moderate □	Severe □		
Abdominal Pain?	□ Yes			□ No	
If yes, is it mild, moderate, or severe?	Mild □	Moderate □	Severe □		
Diarrhea?	□ Yes			□ No	
If yes, is it mild, moderate, or severe?	Mild □	Moderate □	Severe □		
Constipation?	□ Yes			□ No	
If yes, is it mild, moderate, or severe?	Mild □	Moderate □	Severe □		
Nausea/Vomiting?	□ Yes			□ No	
If yes, is it mild, moderate, or severe?	Mild □	Moderate □	Severe □		
Reflux?	□ Yes			□ No	
If yes, is it mild, moderate, or severe?	Mild □	Moderate □	Severe □		
Have you been admitted to hospital since you last received phone communication?	□ Yes			□ No	
General End of Study Questions:					

When answering the following questions, consider how **the last 14 days with Mobility+** have been compared to an average week of using the feeding system that you had **before you started this study**. Please try to answer based **solely on your experience with the Mobility+** in the last two weeks and not on external factors that may have positively/negatively impacted your week of using the Mobility+.

How do you feel your overall Quality of Life has been during the last 2 weeks of using Mobility+?

Excellent	Good	Neutral	Bad	Very Bad
				

How mobile have you been in your everyday activities during the last 2 weeks of using Mobility+, compared to before you started the study?

Much Better	Somewhat Better	About the Same	Somewhat Worse	Much Worse
				

How do you rate the importance of being mobile in your everyday activities to your overall wellbeing?

Very Important	Somewhat important	Not important at all

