4.0 Scoring ratings

A score was given for each rating from 1 to 5, with 5 being the most positive response.

The scoring systems applied were as outlined below:

Patient perspectives on mobility (using current system vs. Mobility+)	Very easy (5) Easy (4) Neutral (3) Difficult (2) Very difficult (1).
Patient perspectives on ease of use	Strongly agree (5) Somewhat agree (4) Neutral (3) Somewhat disagree (2) Strongly disagree (1).
Participant perspective on Quality of life	Excellent (5) Good (4) Neutral (3) Bad (2) Very bad (1)

An overall score for each measure was calculated and averaged for the cohort.

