6.0 Supplemental Baseline data gathered

The following supplemental Baseline Data was gathered at patient enrollment (n=17).

Variables	
Diagnosis, n (%)	
Malignancy	13 (76.5)
GI Dysmotility	2 (11.8)
Bariatric Surgery	1 (5.9)
Functional Disorder	1 (5.9)
Occupation, n (%)	
Working/studying	6 (35.3)
Not working/studying	11 (64.7)
Type of Feeding Tube, n (%)	
G-Tube	14 (82.4)
J-Tube	3 (17.6)
Type of Feeding System before study, n (%)	
Infusion Pump	4 (23.5)
Bolus/Syringe	3 (17.6)
Gravity	7 (41.2)
Combination*	3 (17.6)
Daytime or Night-time Feeds n (%)	
Daytime Only	10 (58.8)
Nighttime Only	1 (5.9)
Both Day & Night-time	6 (35.3)

*Combination was Bolus/syringe, Gravity.

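### The noise item is worded differently at baseline and Day 14, so its before-after change cannot be separated from the change in wording

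*Protocol*

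**What the plan says.** Protocol Appendix 4 (baseline) and Appendix 7 (Day 14) each contain five agreement statements, put to the participant by an operator. On noise, the baseline form has "The noise level of my current system during use (including alarms) is acceptable". The Day 14 form has "The silent nature of The Mobility+ system during use is acceptable".

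Both forms carry the same scoring legend: "Strongly Disagree = 0 points, Somewhat Disagree = 1, Neutral = 2, Somewhat Agree = 3 and Strongly Agree = 4". Protocol 11.2 says "Surveys consist of 16 five-point Likert scale type questions", "meaning the total possible maximum score is 64 points". It compares the total for the usual system with the total for Mobility+, and also allows single questions to be compared. SAP section 4.0 rescales each item to 1 to 5 and labels the agreement scale as ease of use. It adds: "An overall score for each measure was calculated and averaged for the cohort". SAP section 5.0 applies a paired t-test with ANOVA at a 0.05 threshold. Neither document excludes the noise item or treats it separately.

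**The concern.** A paired difference means something only if the same question is asked both times. Here the baseline form asks how acceptable the noise is and names alarms. The Day 14 form tells the participant that the device is silent and asks whether that is acceptable. This repeats the sponsor's own description of the device in Protocol 2.0, and the question is asked aloud by study staff.

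The study has a single arm (Protocol 3.0), so no control group receives the same Day 14 wording to absorb its effect. Two results are exposed: the ease-of-use or overall score that includes the item, and any single-item statement that Mobility+ improved on noise.

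**Working it through.** **1. Are the other items parallel?** The other four agreement statements cover ease of use, ease of carrying, discreet feeding and overall satisfaction. Between Appendix 4 and Appendix 7 they change essentially only the name of the system. The noise statement alone changes what is asked.

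**2. Weight of the item.**
- Stated scale (Protocol 11.2): 16 items × 4 points = 64, which reproduces the plan's maximum. Noise item: 4/64 = 6.3%.
- As printed, each appendix has 9 activity items + 1 work or study item + 5 agreement items = 15, so 60 points. Noise item: 4/60 = 6.7%. When work or study is not applicable, 4/56 = 7.1%.
- Among the agreement items: 1/5 = 20%. SAP 4.0 does not list the items in its ease-of-use measure. That they are these five is inferred from the response labels.
- The move from 0–4 to 1–5 scoring leaves differences unchanged.

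**3. Who had a pump before the study?** SAP 6.0, n = 17: infusion pump 4, gravity 7, bolus/syringe 3, combination 3. The footnote says "Combination was Bolus/syringe, Gravity", so the combination users had no pump. Non-pump users: 7 + 3 + 3 = 13 of 17 (76.5%). Pump users: 4 of 17 (23.5%).

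**4. Size under an assumed wording lift.** The documents give no survey scores. Let the Day 14 wording add d points to the item in m of 17 participants, taking the surveyed number as 17. Then:

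rise in mean total = d × m/17; rise in five-item mean = d × m/(17 × 5)

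| Who shifts | d (assumed) | Rise in mean total | Rise in five-item mean |
|---|---|---|---|
| 4 pump users | 1 | 0.24 | 0.05 |
| 4 pump users | 2 | 0.47 | 0.09 |
| All 17 | 1 | 1 | 0.20 |
| All 17 | 2 | 2 | 0.40 |

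Against the stated 64 points, the all-17 scenario is 1/64 = 1.6% to 2/64 = 3.1% of the scale.

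**5. The item tested alone.** Suppose the four pump users each shift by d and the other 13 do not change. The mean difference is 4d/17 = 0.235d. The variance is d²(4 − 16/17)/16 = 0.191d², so the SD is 0.437d and the standard error is 0.437d/√17 = 0.106d. Then t = 0.235/0.106 = 2.22 on 16 df, two-sided p = 0.041. The d cancels, so this holds for any size of shift. The SAP does not state sidedness; two-sided is assumed. A uniform shift in four people, from whatever cause, would cross the SAP's threshold on this item.

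**The case against.** Several points on the other side stand.

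- **The device may really be silent.** Protocol 2.0 describes it as non-electronic and silent, so pump users may have a true gain on noise. A reader might infer that any gain on this item is an artefact of wording. The documents do not support that: they report no survey scores, so neither a gain nor its wording share is shown.
- **A participant can still disagree.** It is tempting to say that someone who heard noise could not report it. They could choose disagree, and the discreetness and overall-performance items offer another outlet. Disliking silence is also a coherent answer, because the end of a feed is recognised by the pouch deflating, losing weight and ceasing to flow. The Day 14 stem is leading, but it does not guarantee a favourable reply.
- **Non-pump users can answer the baseline item.** A reader might infer that it did not apply to 13 of 17. It asks about noise in general and mentions alarms only in parentheses. A gravity or syringe user can reasonably say that a quiet system is acceptable.
- **The 13 non-pump users limit the bias.** If they already rated noise as acceptable at baseline (an assumption), they had little room to rise. That favours the smaller scenario over the cohort-wide one.
- **The endpoint is secondary.** The primary safety and effectiveness endpoint does not use this survey.

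The listing of both surveys for expert review in Appendix 14 is a weaker defence, since no result or check of item equivalence is given. If the Day 14 item was meant to ask about living without audible signals, it measures something different from baseline, and the difference still cannot be interpreted.

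**Conclusion.** The point holds as a wording mismatch with a likely direction in favour of Mobility+ and an unknown size. Certainty is high that the stems differ and are scored as a pair; it is not high for any amount of bias. Of the scenarios above, the pump-users-only figures are more consistent with the baseline mix of feeding systems, and the all-17 figures are an upper scenario. Both rest on the assumed 1 to 2 point lift and on the five agreement items forming the ease-of-use measure. The effect on the overall score is likely to be small. The single-item comparison is the most exposed, because a small number of participants could decide it. The documents do not support saying that the ease-of-use gain is built in by the wording; they support saying that this item cannot contribute clean evidence to it.

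**What to change.** **For any further use of the forms:** ask one neutral question about the acceptability of the system's noise at both times, without mentioning silence or alarms, changing only the system's name. This is a one-line edit to each form.

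**For data already collected:** the SAP is written after data collection, so a form change cannot help this study. Report the ease-of-use score with five items and with four. Report the overall score with and without the noise item (a maximum of 64 and 60 on the stated scale, or 60 and 56 on the printed items). Label this as a post hoc sensitivity analysis, and state that the item's own before-after change is not interpreted as a noise benefit. Showing both versions is better than dropping the item silently, which would itself be an unplanned change. A split by 4 pump and 13 non-pump users is not recommended: it is unplanned and the groups are too small.

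The cost is a rescoring and a sentence in the report. The reported gain may come out slightly smaller.

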3.0 Purpose

The purpose is to evaluate the safety and effectiveness of Mobility+ enteral feeding system via this initial post-market study (510k clearance number K222678) in adults, a subset of the intended use population. This evaluation will be conducted in a prospective, single arm, non-randomized clinical study.

Hypothesis and Objectives

The study hypothesis is that Mobility+ meets its intended use, safely. The objectives are to evaluate the below primary and secondary endpoints, through execution of this protocol:

Endpoint	Detail	How it will be measured
Primary: Safety and Effectiveness of Mobility+	Evaluate participants who have received familiarization training can use device, according to IFU, to allow delivery of liquid nutrition to their feeding tube, in a real-life setting (home), safely (i.e. can execute critical device use tasks to allow feeding, without serious adverse events) and with effectiveness (i.e. using Mobility+ for the majority or all of their feeding sessions i.e. two daily feeds, minimum)	Phone communication and checklist (Appendix8)

Secondary: Usability of Mobility+	Evaluate Participant perspectives on mobility, ease of use and tolerance, with their current feeding system(s) and Mobility+	Participant perspectives surveys: Baseline (Appendix 4) End of study (Appendix 7)
	Evaluate changes in participant Quality of Life (QoL)	QoL survey at baseline (Appendix 5) and QoL question at end of study (Appendix 7)
	Estimate if participants consume similar average volume (and kcals) of feed/day during the study, compared to baseline	Collect descriptive data on estimated average feed volume and kcals consumed at baseline (Appendix 3) and at end of study (Appendix 8)

The outcome will be presented in a study report.

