Appendix 5**QoL survey**

(Operator asks the Participant these questions)

Reference: Elfadil OM, Patel A, Abdelmagid M, et al. 1117929 - Mental Health Among Enteral Feeding Patients and Caregivers: Is Home Enteral Nutrition Overwhelming? Nutrition and Metabolism Research Oral Paper Session Abstracts. ASPEN Nutrition Science & Practice Conference: March 26-29, 2022 (Seattle, WA). JPEN J Parenter Enteral Nutr. 2022 Mar;46 (S1) <https://aspenjournals.onlinelibrary.wiley.com/doi/full/10.1002/jpen.2344>

Rate your quality of life	Excellent	Good	Neutral	Bad	Very Bad

Appendix 6
Phone Communication check sheet – Trial days

(Operator to use this check sheet to log tubing SKU and changes)

Tubing SKU check								
Trial Day 1: SKU that participant is using: 
 
 440mm RED 	700mm BLUE 	1000mm GREEN 	1900mm WHITE 	
 
					440mm RED 	700mm BLUE 	1000mm GREEN 	1900mm WHITE 
440mm RED 	700mm BLUE 	1000mm GREEN 	1900mm WHITE 					
Select one: 		Stay on this SKU 						
		Trial _____ SKU 						
Reason for changing: <hr/>								
Trial Day 3: SKU that participant is using: 
 
 440mm RED 	700mm BLUE 	1000mm GREEN 	1900mm WHITE 	
 
					440mm RED 	700mm BLUE 	1000mm GREEN 	1900mm WHITE 
440mm RED 	700mm BLUE 	1000mm GREEN 	1900mm WHITE 					
Select one: 		Stay on this SKU 						
		Trial _____ SKU 						
Reason for changing: <hr/>								

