- Advise the participant they can hold their Feeding pouch at times during feeding, to get used to feeling the pouch deflating and reducing in weight

Flushing

- Take the participant through the flushing section of the IFU

Wearing

- Show the participant the IFU guidance on how to loosely coil the giving set tubing and advise them to place the giving set tubing in the bag/clothing they choose to wear the system in (without kinking the tubing).

Hazards

- Ensure the participant is aware of the warning statement and precautions in the IFU

Notes:

- Extension set tubing may be left outside any bag/clothing the device is being worn in
- The Feeding Pouch is not to be squeezed during set up or use. The only time it is appropriate to squeeze the pouch is during flushing

Appendix 12
Participant familiarization training record

Date.....

Participant ID/.....

Operator ID.....

Familiarization training was conducted and the participant was taken through filling (filling method A), feeding, flushing, and wearing, as per the Instructions for Use, and given opportunity to execute the steps necessary for them to use the Mobility+ system at home to obtain their necessary nutrition.

Participant Signature

Operator signature

Appendix 13
Operator training record

Date.....
Operator ID.....

Operator self- training on use of Mobility+ device was conducted.

Operator was trained in execution of this study protocol (CLP001) by the sponsor Rockfield Medical Devices.

Operator signature

Sponsor signature

Appendix 14

Evidence of Expert review

The below specially developed surveys and other study tools are the subject of expert review, which will be recorded in the format of a short report/letter.

Surveys being expertly reviewed for validation:

Participant perspectives surveys:

- Participant perspectives baseline survey (Appendix 4)
- Participant perspectives outcome survey (Appendix 7)

Tools being expertly reviewed for general suitability for use:

- Quality of Life measure (Appendix 5)
- Mobility+ flow rate guide (See LA030 attached to protocol)
- Phone communication check sheets (Trial days – Appendix 6)
- Phone communication check sheets (Study days 7 and 14 - Appendix 8)
- General end of study questions (end of Appendix 7)
- Giving set decision trees (Figures 6 and 7)

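### Quality of life is asked with a different question at baseline and at Day 14 but scored as one measure, so a change cannot be separated from a possible wording effect

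*Protocol*

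**What the plan says.** Protocol 3.0 lists among the secondary endpoints: "Evaluate changes in participant Quality of Life (QoL"). It names a survey at baseline and a question at end of study as the means of measurement, so the use of two instruments is open.

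The baseline item in Appendix 5 is one line, "Rate your quality of life", with five options from Excellent to Very Bad. The Day 14 item in Appendix 7 is "How do you feel your overall Quality of Life has been during the last 2 weeks of using Mobility"+, with the same five options. It stands first under the general end-of-study questions. The preamble to those questions asks for a comparison with an average week on the pre-study system, and for answers based on experience with the device "and not on external factors that may have positively/negatively impacted your week of using the Mobility"+.

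Table 5 (Protocol 11.2) describes the end-of-study element differently. The baseline scale is "accompanied by a simple question evaluating if self-perceived QoL has changed, at end of study", and the analysis is "Evaluate any changes to QoL in the second week of study".

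The Table 4 schedule has a single QoL row, marked at the clinic visit and at the end of the study. SAP 4.0 gives one 1-5 legend for QoL, and SAP 5.0 names a paired t-test with ANOVA at P<0.05, without listing measures. Appendix 14 places the Appendix 5 measure and the general questions under "Tools being expertly reviewed for general suitability for use". It mentions no check that the two QoL items are equivalent.

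**The concern.** A before-after difference has a clear meaning only if the same thing is measured twice. Here the baseline item asks about life as a whole. The Day 14 item fixes a two-week window, ties the answer to the device and comes with an instruction to leave other influences out. Someone whose life has not changed could reasonably give different answers to the two.

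Two features leave nothing to absorb such a shift. The measure is a single item, so a wording shift enters the difference in full. There is also no control group that would share the shift and allow it to be subtracted. What is at stake is the reading of one secondary endpoint: a shift upwards could look like a gain in QoL, and a shift downwards could hide one.

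**Working it through.** **Comparison of the two items**

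| Feature | Baseline (Appendix 5) | Day 14 (Appendix 7) |
|---|---|---|
| Recall period | none stated | last 2 weeks |
| Device named | no | yes |
| Comparison with previous system requested | no | yes, in preamble |
| Told to leave out external factors | no | yes, in preamble |
| Response labels | Excellent to Very Bad | the same |
| Interview (Protocol 8.10, 8.11) | clinic visit | telephone |

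Only the labels agree. Table 5 matches the printed Day 14 item in neither form (a change question against a rating) nor period (the second week against the last 2 weeks).

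**Why the effects cannot be separated.** For each participant, observed difference = true change + wording effect + other before-after influences, including interview mode. One equation per participant with no common item, control group or bridging check does not identify the first two terms.

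**Illustration of size.** The plan gives no power, effect size or SD for QoL, so there is no figure of its own to reproduce. I use n=17 (SAP 6.0 and 7.0, stated for the supplemental data), the named paired t-test, two-sided 0.05 (sidedness is not stated) and no true change.

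Suppose 4 of 17 participants move up one category and 13 do not move:
- mean = 4/17 = 0.235
- SD = sqrt[(4 - 16/17)/16] = 0.437
- t = 0.235/(0.437/sqrt 17) = 2.219 on 16 df, P=0.041
- exact sign test on the four movers: 2 x (1/2)^4 = 0.125

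With three up and none down, the t-test gives P=0.083. If some participants move down:

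| Up / down | Mean | t | P, t-test | P, sign test |
|---|---|---|---|---|
| 4 / 0 | 0.235 | 2.219 | 0.041 | 0.125 |
| 7 / 1 | 0.353 | 2.400 | 0.029 | 0.070 |
| 9 / 2 | 0.412 | 2.384 | 0.030 | 0.065 |

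The sign-test values for the last two rows are 2 x (1+8)/2^8 and 2 x (1+11+55)/2^11.

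In general, the smallest mean difference reaching P<0.05 is 2.120 x SD/sqrt 17 = 0.514 x SD. The chance that a pure wording shift gives P<0.05 follows from the noncentral t with 16 df. The shifts and SDs of change below are assumptions:

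| Assumed SD | Smallest significant mean | Shift 0.25 | Shift 0.5 |
|---|---|---|---|
| 0.5 | 0.26 | 0.49 | 0.97 |
| 0.75 | 0.39 | 0.25 | 0.73 |
| 1.0 | 0.51 | 0.16 | 0.49 |
| 1.5 | 0.77 | 0.10 | 0.25 |

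With no shift the rate is the nominal 0.05. The width of these ranges shows how little the documents fix the size.

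**The case against.** The strongest reply is that the Protocol never promised the same item twice, that the SAP does not say QoL was t-tested, and that no QoL result appears in either document. All of this is correct. Table 5 plans an explicit baseline-to-end score comparison for the perspectives surveys, but for QoL only a baseline determination and an evaluation of change. That the paired test covers QoL is an inference from the single scoring legend, the only named test and the endpoint itself. What survives is that any numerical change score on this legend would compare unlike questions.

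It can also be said that the preamble's request for a comparison lets the Day 14 item serve as the change question of Table 5. On that reading the item already contains a comparison, and subtracting a baseline rating from it makes even less sense.

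The count examples are open to the objection that they show a weakness of the t-test on sparse ordinal data. This stands in part: all three lose significance under the sign test. Moreover, 19 participants were included (SAP 3.0), and no analysis n is given for QoL.

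On expert review, the documents are ambiguous. Protocol 8.11 treats the QoL question as part of the outcome survey, which Appendix 14 lists for validation, whereas the printed item sits among the general questions, which are listed for suitability. Neither route describes an equivalence check.

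Three stronger readings are tempting and are not supported:
- **That a false QoL gain occurred.** Nothing shows that the wording moved any answer, or in which direction.
- **That a separate change question exists.** Table 5 says "The survey consists of 9 simple questions" and eight follow the heading in Appendix 7. The hospital-admission question just above the heading would make nine, so a miscount or the page layout explains this at least as well.
- **That the reworded noise item distorts the ease-of-use score.** Its place in a five-item average is inferred. A 0.25-point shift in it would move the average by 0.05 and give P<0.05 with probability 0.05-0.08 (assumed SD 1.0-0.4), against a nominal 0.05.

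**Conclusion.** The concern holds in a limited form. The two QoL items differ in recall period, attribution and instruction, yet they share one score. In a single-arm study, a change on that score cannot be told apart from a wording effect. This follows from the forms alone and needs no assumed numbers. Its size and direction are unknown, and the figures above illustrate only what a small shift could do at n=17 under the named test.

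The primary safety and effectiveness endpoint, measured with Appendix 8, is not affected. The point is worth correcting because the correction is nearly free, not because the study's main conclusion depends on it.

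**What to change.** For the data already collected:
- Report QoL at baseline and at Day 14 as counts per response category.
- State that the items differ in wording and that the interview moved from clinic to telephone.
- Do not present a paired p-value as evidence of QoL change.

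For any further use of the forms:
- Ask the Appendix 5 item word for word at Day 14, before the general preamble is read out.
- Bring the QoL row of Table 5 into line with the item used, in both form and period.

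The cost is that one secondary result becomes descriptive and gains a sentence of limitation. In future use, one item is added or reworded. No extra participants or visits are needed. Identical wording removes only the wording explanation: the change of interview mode would remain unless it too were aligned, and a before-after difference in a single arm would still not be attributable to the device alone.
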